8.6 Sample size and justification

Main RCT: Taking the number of gout flares to have a negative binomial distribution, we utilized data from the GP care arm of a recently completed nurse-led complex package of care vs. usual-GP care for gout study to calculate (a) expected rate of gout flares in the control arm, (b) expected correlation between number of flares at baseline and during the 2-year study period, and (c) the dispersion parameter [11]. Sample size is based on simulations, using a negative binomial model. The nominal sample size was determined using the formula described by Zhu and Lakkis [45], and implemented in PASS 15 software. Using 90% power and 5% two-tailed significance, and assuming a dispersion parameter of 1.50 (estimated from our recent trial [11] and inflated by 25%), in order to detect a rate ratio of 0.650 (between-group reduction in mean number of flares over 24 months from 3.54 to 2.30), data are required from 190 participants per group. Using 10,000 simulations conducted in R, assuming a correlation between baseline and follow-up rates of flares of 0.33 [11], an adjusted sample size for the inclusion of baseline

Page 52 of 71 Treat to target in gout Protocol Final Version 1.1 date 29 May 2019

flares as a covariate is 186 per group. Allowing for up to 20% loss to follow-up based on our experience of conducting a two-year RCT of gout [11], target recruitment is therefore 233 per group, 466 in total. We chose a rate ratio of 0.650 as this implies a mean between-group reduction of approximately 1 flare of gout over the 2-year study period, assuming an estimated approximate mean 3 acute gout flares in this period in the control arm. This threshold was decided based on PPI input from the two PPI co-applicants (AP, AC) that even one gout flare is so painful that it merits preventing it, if possible. Similar opinion was expressed by a panel of Arthritis Research UK Pain Centre PPI members, comprising of one person with gout, one person with a family member with gout, and six people with other forms of arthritis (April 2017, Nottingham). Results from the recently completed two-year Nurse led care of gout RCT from Nottingham provides reassurance that there will be more than three gout flares in this period [11].

Internal pilot: We will include data from first 90 participants in the internal pilot in order to provide an acceptable level of precision for estimates of proportions in relation to key feasibility outcomes e.g. recruitment rate, drop out-rate. [46]. For a two-sided 95% confidence level, a proportion could be estimated with a margin of error between approximately ± 0.06 and ± 0.08 if the proportion ranged between .1 and .2 (or equivalently, .8 and .9), with such a sample size.

Page 53 of 71 Treat to target in gout Protocol Final Version 1.1 date 29 May 2019

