1. SYNOPSIS

Title	What is the clinical and cost effectiveness of using a goal-directed allopurinol-based treat-to-target protocol in people with recurrent gout flares? Protocol for a randomised controlled trial and internal pilot study
Acronym	T2T
Short title	Treat-to-target in gout
Chief Investigator	[name]
Objectives	Internal pilot : To assess consent rate, attrition, quality of outcome data, delivery of treat-to-target urate-lowering treatment (ULT) and preliminary estimate of the effect of the intervention.
	Full trial: Primary objective: To evaluate the effectiveness of allopurinol-based treat-to-target ULT versus usual general practitioner (GP) care on number of gout flares over two years.
	Secondary objectives: To evaluate the effects of allopurinol-based treat- to-target ULT versus usual GP care on • gout flare severity, • serum urate level, • tophus count, • size of largest tophus, • quality of life, • treatment satisfaction, • drug adherence, • renal function, • adverse events, and • cost-effectiveness Long-term extension: To evaluate the effects of allopurinol-based treat- to-target ULT versus usual GP care on • number of gout flares, • healthcare utilization due to gout, • comorbidities, and
Trial Configuration	eath. Parallal group
	Parallel group
Setting	Primary care
Sample size calculation	Using 90% power and 5% two-tailed significance, and assuming a dispersion parameter of 1.50 to account for variability between participants (estimated from our recent trial, and inflated by 25%), in order to detect a rate ratio of 0.650 (based on mean numbers of flares over 24 months of 3.54 and 2.30 in standard and active arms respectively), 190 participants per group are required for this trial. Using 10,000 simulations conducted in R assuming a negative binomial model, assuming a correlation between baseline and follow-up counts of flares of 0.33, an adjusted sample size for the inclusion of baseline flares as a covariate is 186 per group. Allowing for up to 20% loss to follow-up

Page 5 of 71 Treat to target in gout Protocol Fin Final Version 1.1 date 29 May 2019

	based on our experience of conducting a two-year Nottingham gout treatment trial, target recruitment is therefore 233 per group, 466 in total.
Number of participants	466

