A recent Randomised Controlled Trial (RCT) from Nottingham (n=517) with communitybased recruitment and intervention delivery compared Academic centre based research nurse-led of care to usual (GP-led) care of people with gout over a two year period (11). The nurses were trained about gout and delivered a package of care reflecting recommended best practice (12,13), specifically: individualised holistic assessment with enquiry and discussion of illness perceptions; full information on the nature, causes, possible consequences and treatment options for gout (appendix 3); a treat-to-target ULT strategy; and full patient engagement in management decisions. Compared to usual care, nurse-led care resulted in very high ULT uptake (96% v 56% at year 2); achievement of target serum urate <360µmol/L in more patients (95% v 30% at year 2); lower flare frequency during year 2 (mean 1.5 v 2.4); reduced presence of tophi (3% v 11% at year 2); and improved quality of life (SF-36 physical component) at year 2. The intervention was cost-effective in improving patient-centred outcomes and modelled to be cost-saving at year 5. Flare frequency during year 1 was comparable in both arms (mean 3.6 vs. 3.5) possibly because only 3 participants in the nurse-led arm elected to have flare prophylaxis, even though this option was considered and discussed. Whether such care is generalizable and could be equally well delivered by non-research practice-based nurses, or other health professionals, is unknown. On post hoc analysis, the number of flares over the total two year treatment period were not statistically different between the two arms (MD unpublished data). Thus, it remains unknown if an allopurinol based treat-to-target ULT regime that included flare prophylaxis, reduces the number of gout flares from treatment initiation.

This lack of clarity has resulted in sub-optimal gout management and culminated in discordant recommendations from primary care and rheumatology gout treatment guidelines, exemplified by the recent American College of Physicians' recommendation to treat gout patients to avoid symptoms rather than treat to a target serum urate level, due to lack of high-quality RCT evidence [12–16]. Previous research has demonstrated that gout

Page 14 of 71 Treat to target in gout Protocol Final Version 1.1 date 29 May 2019

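### The 190 per group does not follow from the printed inputs: flare means of 3.54 and 2.30 over 24 months give about 205 to 211, and the time unit of these means needs reconciling

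*Protocol*

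**What the plan says.** Protocol section 8.6 names the method: "The nominal sample size was determined using the formula described by Zhu and Lakkis [45], and implemented in PASS 15 software". The error rates are "Using 90% power and 5% two-tailed significance". The dispersion is set by "assuming a dispersion parameter of 1.50 (estimated from our recent trial [11] and inflated by 25"%), so 1.50 already contains the inflation. The effect is a rate ratio of 0.650, described as a "between-group reduction in mean number of flares over 24 months from 3.54 to 2.30), data are required from 190 participants per group". The synopsis gives the same time frame: "mean numbers of flares over 24 months of 3.54 and 2.30 in standard and active arms respectively".

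A separate R simulation, which adds the baseline flare count as a covariate with correlation 0.33, lowers 190 to 186. A 20% loss to follow-up then gives 233 per group, 466 in total.

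Section 8.6 takes the control rate from the usual-care arm of the earlier nurse-led trial. Section 3 reports that trial with the nurse-led arm first: "Flare frequency during year 1 was comparable in both arms (mean 3.6 vs. 3.5") and "lower flare frequency during year 2 (mean 1.5 v 2.4"). Section 8.6 also defends the rate ratio on the ground that "this implies a mean between-group reduction of approximately 1 flare of gout over the 2-year study period", on the assumption of roughly 3 control-arm flares in that period.

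**The concern.** The protocol prints every input that the formula needs, so 190 can be checked directly, and it does not come out. The printed 24-month control mean of 3.54 is also well below the 24-month total of the arm it is said to come from, and close to that arm's year 1 mean of 3.5.

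Two things depend on the answer. The first is the power claim: with fewer expected flares, each participant contributes less information and more participants are needed. The second is the target difference. The printed means differ by 1.24 flares, which fits the patient-supported rationale of about one flare prevented. Means that yield about 190 would imply a larger absolute reduction. As printed, the means, the 190 and the rationale cannot all stand.

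**Working it through.** **Inputs.** Means 3.54 and 2.30 over 24 months, rate ratio RR = 0.650, dispersion k = 1.50, two-sided 5% (z = 1.960) and 90% power (z = 1.2816), all from section 8.6. Allocation is 1:1 (section 6.4.1).

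**Formula (Zhu and Lakkis, equal groups).**

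n per group = (1.960·√V0 + 1.2816·√V1)² / (ln RR)²

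V1 = (1/T)(1/r0 + 1/r1) + 2k, and (ln 0.650)² = 0.1856.

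V0 is the variance under the null. It has three options: both arms at the control rate, both arms at their true rates, or the maximum-likelihood version, which uses the average rate. The protocol does not say which was used, so all three are shown.

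**Step 1: attempt to reproduce 190 from the inputs as printed (means over 24 months, T = 1).**

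V1 = 1/3.54 + 1/2.30 + 3.00 = 0.282 + 0.435 + 3.00 = 3.717

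| Null variance | V0 | n per group |
|---|---|---|
| Control rate | 3.565 | 205.2 |
| True rates | 3.717 | 210.5 |
| Maximum likelihood | 3.685 | 209.4 |

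No option gives 190.

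**Step 2: other entries.**

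| Entry | n per group, three options |
|---|---|
| 3.54 and 2.30 as yearly rates, T = 2 (7.08 v 4.60 over 24 months) | 187.6 / 190.2 / 189.6 |
| 24-month control mean 5.9, RR 0.650 | 191.1 / 194.2 / 193.6 |
| 24-month control mean 3, RR 0.650 | 211.6 / 217.8 / 216.5 |
| Printed means, k = 1.20 (1.50/1.25) | 171.3 / 176.5 / 175.4 |
| Printed means, k = 1.875 (1.50 × 1.25) | 247.7 / 252.9 / 251.8 |
| Printed means, 80% power | 152.7 / 157.2 / 156.3 |
| Printed means, one-sided 5% | 167.6 / 171.5 / 170.7 |

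The yearly-rate entry is the one that lands on 190. With the printed means, a dispersion of about 1.32 would also be needed to reach 190 (true-rates option), and the protocol gives no such value.

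**Step 3: comparison with the source trial.** The usual-care means in section 3 are 3.5 in year 1 and 2.4 in year 2, so 3.5 + 2.4 = 5.9 over 24 months. The printed 3.54 agrees with the year 1 figure, not with the 24-month sum.

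**Step 4: implied reduction in flares.**
- Printed means: 3.54 − 2.30 = 1.24.
- Control mean 5.9: 0.35 × 5.9 ≈ 2.1.
- Yearly-rate reading: 7.08 − 4.60 = 2.48.

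**Step 5: power at the printed means.** Inverting the formula gives 86.2-87.0% at 186 per group and 86.9-87.7% at 190.

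The covariate-adjusted power has to be simulated, because the protocol does not state the inputs of its own simulation. The assumptions made here are gamma-distributed participant rates linked by a Gaussian copula, a baseline mean of 2 to 4.2, a correlation of about 0.33, and a baseline count entered linearly or as a log.
- 1.50 as the marginal dispersion: about 88-89% at 186 per group (runs from 87.5% to 90%).
- 1.50 as the dispersion left after adjustment: about 84-85%.
- Baseline counts forced to be non-zero: 92-93%, but the marginal dispersion in those runs fell to about 1.15-1.18, so they do not test the printed 1.50.
- 24-month control mean of 5.9 with marginal dispersion 1.50: about 91-92%.

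**Step 6: dropout.** 186/0.8 = 232.5, rounded up to 233. This step is correct given 186.

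**The case against.** The strongest defence is that 190 is only a nominal figure. Section 8.6 says that the sample size rests on simulations, and 466 comes from 186, the covariate-adjusted result. Setting an unadjusted 210 against an adjusted 186 does not compare like with like. This stands. A reader might infer that 466 fails to give 90% power, or that the trial must grow: scaling 210 by 186/190 gives about 206 evaluable per group, and 206/0.8 = 257.5, so 258 per group or 516 in total. The documents do not support either conclusion, because the baseline mean, the covariate form and the kind of dispersion in that simulation are not given, and adjusted power could reach 90% on some choices.

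Secondly, the error may lie in the label rather than in the number. With a 24-month control mean of 5.9 the formula gives 191 to 194 and 466 is about adequate. This also stands, but then the printed 24-month means are wrong.

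Thirdly, a reader might infer that the two-year exposure was applied twice in the software. That fits the numbers, but nobody can see the entry. A mean of 5.9 also comes close to 190, as does a dispersion of 1.32, so the cause remains an inference.

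Fourthly, the mean of roughly 3 in the rationale is a rounded figure. A 35% reduction is 1.05 flares from 3 and 1.24 from 3.54, both fairly about one. It is not strong evidence of a rival input.

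Finally, the 25% inflation of the dispersion leaves a margin: at 1.20 the unadjusted formula gives about 91-92% power at 186 per group. That softens the practical consequence, but 1.50 is the planning value on which the protocol claims 90%.

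**Conclusion.** The sample size statement is wrong as written. The printed 24-month means, dispersion, power and significance level give about 205 to 211 per group under every null-variance option, against a stated 190. The difference is 15 to 21 per group before covariate adjustment and dropout. This is arithmetic on the protocol's own inputs and needs no outside assumption. That the cause is a time-unit error is likely, given the 188 to 191 on the yearly-rate reading and the 5.9 flares in the source arm, but it is not proven.

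At the printed means, 90% power is not demonstrated. Power at 186 evaluable per group is about 86-87% unadjusted and roughly 84-90% adjusted. The adjusted range depends on whether 1.50 is the marginal or the conditional dispersion, and on the simulation assumptions listed above. Whether 466 is too small depends on which control mean is right, and the documents do not settle that.

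**What to change.** - State the control and active means on one time base, and say whether 3.54 and 2.30 are per year or per 24 months.
- Reconcile them with the source trial's 3.5 and 2.4 flares in section 3 and with the rationale of about one flare prevented.
- Rerun the formula, naming the null-variance option, and the covariate simulation. State the simulation's baseline mean, covariate form and kind of dispersion.
- Correct section 8.6 and the synopsis together.

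If the 24-month means stand, replace 190 by about 210 and restate the power of 466 from the rerun (about 86-87% before covariate adjustment). If they are annual rates, print 7.08 and 4.60 over 24 months and change the stated reduction to about 2.5 flares. If the 24-month control mean is nearer 5.9, print that mean with the matching active mean and reduction.

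The cost is one rerun and rewording in two places, with possibly a slightly lower stated power. Correcting the statement does not require more recruitment.

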8.7 Assessment of efficacy

Table 12: Assessment of efficacy

Endpoints	Efficacy parameter	Timing	Timing
		RCT	extension
Primary			
Number of gout flares	Rate ratio	2 year	4 year
Secondary			
Pain severity during flare	Mean difference	2 year	4 year
Duration of flare	Mean difference	2 year	4 year
Generic HR-QoL (EQ-5D-5L) during flare	Mean difference	During flare	NA
Gout specific HR-QoL (GIS) during flare	Mean difference	During flare	
EQ-5D-5L HR-QoL between flares	Mean difference	1, 2 year	NA
Serum urate	Mean difference	2 year	NA
Serum creatinine and estimated GFR	Mean difference	2 year	NA
Urine albumin creatinine ratio	Mean difference	2 year	NA
Medication possession ratio	Mean difference	2 year	
Treatment acceptability questionnaire	Mean difference	2 year	
Healthcare utilization		2 year	4 year
Primary care consultations for gout	Mean difference	2 year	4 year
Hospitalizations due to gout flares	Mean difference	2 year	4 year
Current ULT		2 year	4 year
Number of ULT prescriptions	Mean difference		
No of prescriptions for treating flares	Mean difference	2 year	4 year
Cost-effectiveness		2 year	NA
Comorbidities			
Death	Hazard ratio	2 year	4 year
Chronic kidney disease progression	Hazard ratio	2 year	4 year
Ischaemic heart disease	Hazard ratio	2 year	4 year
Myocardial infarction	Hazard ratio	2 year	4 year
Stroke	Hazard ratio	2 year	4 year

median difference or rate ratio will replace mean difference, if appropriate

Page 54 of 71

Treat to target in gout Protocol Final Version 1.1 date 29 May 2019

8.8 Assessment of safety

Given the fact that the drugs and interventions used in this study have been used in routine clinical practice for several decades, safety data will be reviewed by the DMC annually, and summarised over the whole trial period.

Table 12	Accoment	~ f	a of other	
Table 13	Assessment	O I	Salety	

Endpoints	Timing RCT
Adverse events	2 year
Serious adverse events	2 year
ULT discontinuation due to adverse events	2 year

8.9 Procedures for missing, unused and spurious data

Patterns of missingness will be explored, maximum likelihood estimation based on all the available data is not affected if outcome data are missing at random. Multiple imputation will be used for explanatory variables if missing at random is a plausible assumption.

8.10 Definition of populations analysed

Safety set: All randomized participants who received at least one treatment.

Full analysis set: All randomized participants.

Adherers-only set: All participants who received the treatment to which they were randomized as prescribed in the protocol.

As-treated set: All participants who received at least one treatment.

9. ADVERSE EVENTS

9.1 Definitions

An adverse event is any unfavourable and unintended sign, symptom, syndrome or illness that develops or worsens during the period of observation in the study.

An AE does include:

1. exacerbation of a pre-existing illness.

2. increase in frequency or intensity of a pre-existing episodic event or condition.

3. condition detected or diagnosed after medicinal product administration even though it may have been present prior to the start of the study.

4. continuous persistent disease or symptoms present at baseline that worsen following the start of the study.

Page 55 of 71 Treat to target in gout Protocol Final Version 1.1 date 29 May 2019

Adverse events that are known side-effects of ULT, flare prophylaxis or omeprazole will be classed as adverse events and do not require reporting, unless they meet the criteria of related-unexpected serious adverse event (SAE), see below.

An AE does not include:

1. medical or surgical procedure (e.g., surgery, endoscopy, tooth extraction, transfusion); but the condition that lead to the procedure is an AE.

2. a pre-existing disease or condition present or detected at the start of the study that did not worsen.

3. situations where an untoward medical occurrence has not occurred (e.g., hospitalizations for elective surgery, social and/or convenience admissions).

4. disease or disorder being studied or sign or symptom associated with the disease or disorder unless more severe than expected for the participant's condition.

5. overdose of concurrent medication without any signs or symptoms.

A SAE is any adverse event occurring following study mandated procedures, after receipt of the treatment or intervention that results in any of the following outcomes:

1. Death

- 2. A life-threatening adverse event
- 3. Inpatient hospitalization or prolongation of existing hospitalization
- 4. A disability / incapacity
- 5. A congenital anomaly in the offspring of a participant

Important medical events that may not result in death, be life-threatening, or require hospitalization may be considered a serious adverse event when, based upon appropriate medical judgment, they may jeopardize the patient or participant and may require medical or surgical intervention to prevent one of the outcomes listed in this definition

All adverse events will be assessed for seriousness, expectedness and causality:

A distinction is drawn between serious and severe AEs. Severity is a measure of intensity whereas seriousness is defined using the criteria above. Hence, a severe AE need not necessarily be serious.

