Very rare: diabetes mellitus, hyperlipidaemia

Frequency not known: exacerbation of gout flares

Psychiatric disorders

Very rare: depression,

Nervous system disorders

Very rare: ataxia, coma, headache, neuropathy, paraesthesia, paralysis, somnolence, taste perversion, dysgeusia

Frequency not known: dizziness

Page 18 of 71

Treat to target in gout Protocol Final Version 1.1 date 29 May 2019

Eye disorders

Very rare: cataract, macular changes, visual disorders

Ear and labyrinth disorders

Very rare: vertigo

Cardiac disorders

Very rare: angina, bradycardia

Vascular disorders

Very rare: hypertension

Frequency not known: vasculitis

Gastrointestinal disorders

Uncommon: nausea, vomiting

Very rare: changed bowel habit, stomatitis, steatorrhoea, haematemesis

Frequency not known: diarrhoea, abdominal pain,

Hepatobiliary disorders

Uncommon: asymptomatic increases in liver function tests

Rare: Hepatitis (including hepatic necrosis and granulomatous hepatitis)

Skin and subcutaneous tissue disorders

Common: rash

Rare: Severe cutaneous adverse reactions (SCARs): Stevens-Johnson syndrome (SJS) and toxicepidermal necrolysis (TEN) have been reported (see section 4.4). The highest risk for SJS and TEN, or other serious hypersensitivity reactions, is within the first weeks of treatment.

Very Rare: alopecia, angioedema, discoloured hair, fixed drug eruptions.

Frequency not known: skin reaction associated with eosinophilia, urticaria.

Drug Rash with Eosinophilia and Systemic Symptoms (DRESS) has been reported. Some cases have had a fatal outcome.

Skin reactions are the most common reactions and may occur at any time during treatment. They may be pruritic, maculopapular, sometimes scaly or purpuric, associated with

> Page 19 of 71 Treat to target in gout Protocol Final Version 1.1 date 29 May 2019

exfoliation, fever, lymphadenopathy, arthralgia and/or eosinophilia resembling Stevens-Johnson syndrome (SJS), toxic epidermal necrolysis (TEN) and/or Lyell's. Allopurinol should be withdrawn immediately should such reactions occur.

If desired, after recovery from mild reactions, allopurinol may be reintroduced at a low dose (e.g. 50mg/day), which may be gradually increased. If the rash recurs, allopurinol should be permanently withdrawn.

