The HLA-B*5801 allele has been identified as a genetic risk factor for allopurinol associated SJS/TEN in retrospective, case-control, pharmacogenetic studies in patients of Han Chinese, Japanese and European descent. Up to 20–30% of some Han Chinese, African and Indian populations carry the HLA-B*5801 allele whereas only 1–2% of Northern European, US European and Japanese patients are estimated to be HLA-B*5801 carriers. However, the use of genotyping as a screening tool to make decisions about treatment with allopurinol has not been established.

The clinical diagnosis of SJS/TEN remains the basis for decision making. If such reactions occur at any time during treatment, allopurinol should be withdrawn immediately and permanently.

Renal and urinary disorders

Very rare: haematuria, uraemia, azotaemia

Frequency not known: nephrolithiasis

Reproductive system and breast disorders

Very rare: gynaecomastia, impotence, infertility, erectile dysfunction

Frequency not known: nocturnal emissions

General disorders and administration site conditions

Very rare: asthenia, general malaise, oedema, pyrexia*

Investigations

Common: blood thyroid stimulating hormone increased**

* Fever has been reported to occur with and without signs and symptoms of a more generalized allopurinol hypersensitivity reaction.

** The occurrence of increased thyroid stimulating hormone (TSH) in the relevant studies did not report any impact on free T4 levels or had TSH levels indicative of subclinical hypothyroidism.

Table 3 Side effects to Febuxostat

Within each frequency grouping, adverse reactions are presented in order of decreasing seriousness.

Blood and lymphatic system disorders

Rare: Pancytopenia, thrombocytopenia, agranulocytosis

Immune system disorders

Rare: Anaphylactic reaction, drug hypersensitivity

Endocrine disorders

Uncommon: Blood thyroid stimulating hormone increased

Eye disorders

Rare: Blurred vision

Metabolism and nutrition disorders

Common: Gout flares

Uncommon: Diabetes mellitus, hyperlipidemia, decrease appetite, weight increase

Rare: Weight decrease, increase appetite, anorexia

Psychiatric disorders

Uncommon: Libido decreased, insomnia

Rare: Nervousness

Nervous system disorders

Common: Headache

Uncommon: Dizziness, paraesthesia, hemiparesis, somnolence, altered taste, hypoaesthesia, hyposmia

Ear and labyrinth disorders

Rare: Tinnitus

Cardiac disorders

Page 21 of 71 Treat to target in gout Protocol Final Version 1.1 date 29 May 2019

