9.4 Trial Treatment / Intervention Related SAEs

A serious adverse event that is unexpected in its severity and seriousness *and* deemed directly related to or suspected to be related to the trial treatment or intervention shall be reported to the ethics committee that gave a favourable opinion as stated below. The event shall be reported immediately of knowledge of its occurrence to the Chief Investigator.

The Chief Investigator will:

• Assess the event for seriousness, expectedness and relatedness to the trial treatment or intervention.

Page 57 of 71 Treat to target in gout Protocol Final Version 1.1 date 29 May 2019

- Take appropriate medical action, which may include halting the trial, and inform the Sponsor of such action.
- If the event is deemed related to the trial treatment or intervention, inform the REC using the reporting form found on the HRA web page within 7 days of knowledge of the event.
- Within a further eight days send any follow-up information and reports to the REC.
- Make any amendments as required to the study protocol and inform the REC as required

Expected SAEs such as hospitalization due to gout flare, side-effects of ULT or flare prophylaxis e.g. diarrhoea due to colchicine will not be reported to the ethics committee.

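### Sections 9.1 and 9.4 give conflicting rules on whether a gout flare is an adverse event, and no rule is said to prevail

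*Protocol*

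**What the plan says.** All places are in the protocol.

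**Rules that bring a flare in**
- The general definition in 9.1: "An adverse event is any unfavourable and unintended sign, symptom, syndrome or illness that develops or worsens during the period of observation in the study".
- The second inclusion item in 9.1: "increase in frequency or intensity of a pre-existing episodic event or condition". Gout is such a condition.
- The rule on drug reactions in 9.1: "Adverse events that are known side-effects of ULT, flare prophylaxis or omeprazole will be classed as adverse events and do not require reporting". Section 5.6 lists flares for both main drugs: for allopurinol (Table 2), "Frequency not known: exacerbation of gout flares"; for febuxostat (Table 3), "Common: Gout flares".

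**Rule that keeps a flare out**
- The fourth exclusion item in 9.1: "disease or disorder being studied or sign or symptom associated with the disease or disorder unless more severe than expected".

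**Rule on serious events**
- Section 9.1 defines an SAE as an adverse event that has one of the listed outcomes, inpatient admission among them.
- Section 9.4 speaks of "Expected SAEs such as hospitalization due to gout flare" as events that need not go to the ethics committee.

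**Where the counts are used**
- Section 6.1.2 lists AEs as a secondary outcome. Section 6.1.3 names intervention-related AEs, and stopping because of them, as the safety outcomes.
- Section 8.3 plans to tabulate side-effects of the intervention and compare them between groups.
- Table 13 in 8.8 lists AEs and SAEs as safety endpoints, and the data monitoring committee reviews safety data every year.

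**The concern.** The protocol itself expects more flares when ULT is started. Section 7.1 gives this as the reason for prophylaxis, and section 8.2 says it is why early flares cannot serve as a signal of efficacy. The harm most closely tied to the intervention is therefore the event on which the AE rules disagree.

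Two consequences follow. First, one flare can be logged as an AE and a side-effect of ULT at one practice and left out at another. Secondly, the choice need not be neutral between arms. Sections 6.4.1 and 6.4.2 make clear that the GP and usual care team know the allocation, and a flare soon after a dose change in the intervention arm invites the side-effect label more readily than a flare under usual care. The AE, SAE and side-effect counts would then partly reflect classification practice. These counts reach the data monitoring committee, and section 7.11 allows major safety concerns to stop the trial.

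**Working it through.** The point is textual, and the protocol states no figure for it that could be reproduced. The check is to take each kind of flare through each rule.

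| Event | Inclusion rules in 9.1 | Exclusion rule in 9.1 | Section 9.4 | Consistent? |
|---|---|---|---|---|
| Flare of greater severity than expected | AE | AE (exception applies) | – | Yes |
| Flares of usual severity, but more often than before | AE (second inclusion item) | Not an AE | – | No |
| Flare of usual severity attributed to allopurinol or febuxostat | AE (known side-effect) | Not an AE | – | No |
| Admission for a flare of usual severity | AE, hence SAE, if either of the two rows above applies | Not an AE, hence not an SAE | Expected SAE | No |

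The exception cannot be stretched to cover frequency. Section 9.1 describes severity as intensity, and the second inclusion item names frequency and intensity as separate things. Nor can seriousness stand in for severity, because 9.1 separates the two.

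**Upper bound on the number of events affected**

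Inputs from section 8.6: mean flares over 24 months of 3.54 (control) and 2.30 (intervention); 233 recruited per arm; 186 per arm needed after the 20% allowance for loss.

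Events = participants × mean flares:
- 233 × 3.54 = 824.8, about 825; 233 × 2.30 = 535.9, about 536; difference about 289.
- With 186 per arm: 186 × 3.54 = 658.4 and 186 × 2.30 = 427.8.

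These counts treat every flare as an AE and, at 233, assume complete follow-up. The second inclusion item reaches only increases, so the true number in dispute is smaller, by an amount that the protocol does not allow one to calculate.

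**What the extreme reading could do to an AE ratio (assumptions, not protocol figures)**

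Let b be the non-flare AEs per control participant over 24 months, and R the true intervention-to-control ratio of non-flare AEs. The protocol gives neither. With every flare counted, the AE rate ratio is (b × R + 2.30) / (b + 3.54).

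| b | R = 1 | R = 1.5 |
|---|---|---|
| 0.5 | 2.80 / 4.04 = 0.693 | 3.05 / 4.04 = 0.755 |
| 1 | 3.30 / 4.54 = 0.727 | 3.80 / 4.54 = 0.837 |
| 2 | 4.30 / 5.54 = 0.776 | 5.30 / 5.54 = 0.957 |

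Without flares the ratios would be 1.00 and 1.50. The table shows the direction of the distortion at the upper bound and is not a forecast.

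**The case against.** **The specific clause may override the general ones.** On this reading a flare is not an AE unless unusually severe, and a flare that needs admission can be judged unusually severe, which fits 9.4. This is the best reconciliation and it settles part of the conflict. It leaves three gaps: more frequent flares of usual severity, flares that Tables 2 and 3 make known side-effects, and an admitted flare of usual severity. The protocol does not state this order of precedence.

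**A reader might infer that Table 13 sets the arms against each other on all AEs, so that preventing flares would decide the safety result.** The text does not support this. Table 13 lists endpoints and a time point. The between-group comparison that is stated, in 8.3, concerns side-effects of the intervention, and most flares under usual care would not be that. The 825 and 536 therefore should not be read as counts entering a planned comparison. In addition, 9.1 exempts known side-effects from reporting unless they are related, unexpected SAEs.

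**A reader might infer that provoked flares vanish from view.** They do not. All qualifying flares are in the primary outcome, section 6.1.2 adds counts for months 1–12 and 13–24, and hospitalizations for gout are a listed outcome. Any loss is confined to the safety tables and safety review.

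**A reader might try to size the SAE effect from the admissions quoted in section 3.** Those figures mix different years (2008–2009 and 2007) and areas (England; England and Wales). Taking all 7,916 admissions or only the 3,496 emergencies changes the answer by a factor of 7,916 / 3,496 = 2.3. No usable flare-admission rate follows for this population.

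**Seriousness and causality are not left to sites alone.** Under 9.3 the chief investigator determines them with the treating practitioners. This helps for SAEs that are notified, but not for the prior question of whether a flare is an AE at all.

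**Conclusion.** The contradiction is real and lies in the protocol's own definitions, so it is not a detail that can be left to the statistical analysis plan. Section 9.1 both includes and excludes flares that become more frequent or are attributed to ULT, and 9.4 names as an SAE an event that the exclusion in 9.1 would stop from being an AE. Which flares enter the AE, SAE and side-effect counts can therefore differ by site and by arm.

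The effect on those counts cannot be quantified from the protocol, which gives no non-flare AE rate and no flare-admission rate. The only bound is that at most all flares are in dispute: 825 and 536 at the planning means with 233 fully followed per arm. The primary analysis is untouched. The point should be corrected because the safety counts are open to differential classification and the remedy is cheap. It does not show that the safety conclusions would be decided by efficacy.

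**What to change.** Reconcile 9.1 and 9.4 into one recording rule that applies identically in both arms. For example:

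- Flares are recorded as the efficacy outcome, and not as AEs or as side-effects of ULT, whatever their frequency or presumed cause.
- As an explicit exception to that exclusion, a flare that meets a seriousness criterion is recorded as an SAE and classed as expected. Without this sentence the rule would repeat the present conflict, because an SAE must be an AE.
- Section 9.1 says that this rule takes precedence over the second inclusion item, the clause on known side-effects and the flare entries in Tables 2 and 3.
- AE and SAE totals are reported without flares, with flare SAEs on a separate line by arm. The layout can be placed in the statistical analysis plan.

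The cost is wording in 9.1 and 9.4 and a note to sites on completing the AE and side-effect fields. Flares and admissions for gout, with dates, are already collected under 7.7 and 7.8, so no new data are needed and patient care does not change.
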